8.2. Treatment Phase

8.2.1. Treatment Visits

8.2.1.1. C1D1 Ibrutinib

Required testing for the visit:

- CBC with differential
- Comprehensive metabolic panel

Blood count and hepatic function criteria for dosing will be verified.

8.2.2. Response Follow-up

Required testing for the response follow-up visits (months 1, 2, 3, 6, 9, 12):

- Medical history
- Physical examination, including vital signs, weight, and Karnofsky performance status
- Laboratory evaluation per institutional guidelines including CBC with differential, glucose, BUN, creatinine, total bilirubin, alkaline phosphatase, LDH, albumin, SGOT(AST), SGPT (ALT), CRP, CK, calcium, and magnesium.
- Biomarkers (correlative lab studies)
- Documentation of concomitant medications
- Completion of institutional GVHD assessment form (see Appendix E)
- Completion of a GVHD patient self-report form (see Appendix F)
- Document cumulative corticosteroid use
- Document any new systemic IST and reason for use

- Document treatment-emergent toxicities and adverse events
- Document any IVIG use
- PFTs (at 3, 6, 9 and 12 month visits only)

9. SUBJECT COMPLETION AND WITHDRAWAL

9.1. Completion

Patients will be considered to be off study if any new systemic immunosuppressant therapy (including ECP) to treat worsening cGVHD is received. No subsequent adverse or serious adverse event reporting will be done. Further follow up off study will be according to institutional requirements.

Patients will be considered to have completed study follow up at 12 months or 30 days after the last dose of ibrutinib whichever comes last. Further off study follow up will be according to institutional requirements.

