Statistical Methods/ Data Analysis: Refer to Section 10 for additional details.	
This is a phase II trial evaluating the safety and efficacy of ibrutinib and rituximab as primary treatment of cGVHD. We plan to enroll 35 patients on this study. Patients will be formally monitored for 12 months to evaluate for outcome and safety endpoints. All patients, responders and treatment failures, will be followed for a period of one year. The primary outcome measure will be the proportion of patients that are alive and off systemic immunosuppression therapies (IST) at 12 months following initiation of treatment. Secondary outcome measures will be cGVHD response, cumulative steroid exposure, time to discontinuation of systemic immunosuppression, requirement for second-line GVHD therapy, non-relapse and overall mortality, and safety.

Sample Size Determination	
The study will be powered to detect a clinically meaningful improvement in treatment success at 12 months post-treatment, defined as being alive and off all systemic immunosuppression. Experience from our phase II study of rituximab in the upfront treatment of cGVHD found that 56% of patients were alive and free of systemic immunosuppression at 12 months post treatment. It is hoped that under this protocol, this rate will be at least 75%. Thus we statistically formalize this study by testing the null hypothesis that p, the treatment success rate is 0.55 or less versus the alternative hypothesis that p is at least 0.75. A sample size of 35 patients gives 80% power with an $\alpha=0.05$, using the formula for a one sample binomial (one-sided) test of a proportion.

----------------------------------	--

ABBREVIATIONS

AE	adverse event
AESI	adverse events of special interest
ALT	alanine aminotransferase
ANC	absolute neutrophil count
ASCO	American Society of Clinical Oncology
AST	aspartate aminotransferase
AUC	area under the concentration-time curve
BCR	B-cell receptor
BTK	Bruton's tyrosine kinase
CLL	chronic lymphocytic leukemia
C _{max}	maximum observed plasma concentration
CR	complete response
CrCl	creatinine clearance
CRF	case report form (paper or electronic as appropriate for this study)
CT	computed tomography
CTCAE	NCI Common Terminology Criteria for Adverse Events
CYP	cytochrome P450
DMC	Data Monitoring Committee
ECOG	Eastern Cooperative Oncology Group
ECG	electrocardiogram
EDC	electronic data capture
FDA	Food and Drug Administration
GCP	Good Clinical Practice

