3. STUDY DESIGN

3.1. Overview of Study Design

The rationale for the study concept is provided in [Section 1.3](#).

This is a phase II trial evaluating the safety and efficacy of the combination of Ibrutinib and Rituximab as primary treatment of cGVHD. We plan to enroll 35 patients on this study. Patients will be formally monitored monthly for 12 months to evaluate for outcome and safety endpoints. All other assessments will be done at the physician's discretion or institutional standards. All patients, responders and treatment failures, will be followed for a period of one year from the time of initiation of therapy. The primary endpoint will be the proportion of patients that are alive and off all systemic IST at 12 months following initiation of treatment.

Eligible patients will be those with a first episode of symptomatic cGVHD, requiring systemic immunosuppression for control of symptoms. Following study entry, patients will be started on:

[figure not shown]
1. Ibrutinib 420mg PO QDAY (28-day cycles) for a total of 12 cycles unless discontinued early due to toxicity (see stopping rules in section 5.1.1.4). Dose adjustments are required for patients with hepatic impairment or those receiving concomitant voriconazole or posaconazole or other strong CyP 3A4 inhibitor according to sections 5.1.1.5 and 5.1.1.6.
2. Rituximab 375mg/m² IV weekly x 4 weeks (to be started on study day 7 ± 3 days), then 375mg/m² IV q3months x 4 doses (months 4, 7, 10, 13).

Additional cGVHD treatment will include:

- **Sirolimus** (target level 4-10 ng/mL) – patients currently receiving a calcineurin inhibitor (tacrolimus or cyclosporine) and/or mycophenolate mofetil for GVHD prophylaxis will be converted to sirolimus per institutional guidelines. In the case of contraindication or intolerance to sirolimus, another systemic immunosuppressive (IS) drug (i.e. tacrolimus or cyclosporine) may be substituted at the discretion of the treating investigator.
- Short-course corticosteroids may be used, if necessary, for more rapid symptom control (≤1mg/kg Medrol, with planned taper to be completed no longer than 4 weeks).

When cGVHD manifestations have been quiescent for at least 4 weeks, sirolimus (or other IS medication) should be tapered over 4 weeks or per investigator discretion.

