6.3. Other Systemic Immunosuppression Therapy for cGVHD

Addition of any new systemic immunosuppressant therapy (including ECP) to treat worsening cGVHD is prohibited. This will be considered a treatment failure, patient will be removed from study and treated according to institutional standard-of-care.

Any increase in the dose of methylprednisolone (or equivalent) and any resumption of treatment with methylprednisolone, after previous discontinuation, is not considered as secondary systemic therapy.

Any increase in the dose of sirolimus or calcineurin inhibitor, or resumption of treatment following discontinuation, is not considered as secondary systemic therapy, if the treatment in question was included in the immunosuppressive regimen at study initiation.

A substitution of the systemic immunosuppressant drug (e.g. tacrolimus for sirolimus) for reasons other than cGVHD progression (e.g. toxicity) may be permitted after discussion with the principal investigator and is not considered as secondary systemic therapy.

Topical therapy, including steroid creams, topical tacrolimus, oral budesonide, inhaled steroids and ophthalmic solutions are not considered as secondary therapy.

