10. STATISTICAL METHODS AND ANALYSES

10.1. Analysis Population

All treated subjects

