10.2.2. Secondary Endpoints

Secondary efficacy endpoints:

To estimate:

- Chronic GVHD response (CR + PR, both individual organ response and overall response, according to 2014 NIH Response Criteria Working Group Report) – See Appendix G.
- Cumulative steroid exposure (total mg methylprednisolone or equivalent).
- Time to discontinuation of systemic immunosuppression (defined as the date that all systemic IST has been discontinued after resolution of all reversible manifestations of cGVHD. Discontinuation of immunosuppressive medications for the purpose of inducing an anti-tumor response after the development of recurrent or secondary malignancy will not be counted as successful discontinuation of IST).
- Failure-free survival (defined as being alive without the requirement for second-line cGVHD therapy). See section 6.3 for definition of second-line cGVHD therapy.
- Non-relapse and overall mortality

Safety endpoints:

To estimate:

- Incidence of grade ≥ 3 adverse events, possibly or probably related to either ibrutinib and/or rituximab.

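### Sections 6.3 and 9.1 take treatment failures off study although one-year follow-up is promised for them, so their later vital status and steroid use are not required data, and 9.1 also conflicts with 7.1.1.5 and 11.4.2 on safety reporting

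*Combined protocol and SAP*

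**What the plan says.** **Follow-up promised.** Section 3.1 states: "All patients, responders and treatment failures, will be followed for a period of one year from the time of initiation of therapy". The synopsis (Statistical Methods) and section 10.4 repeat it: "All patients, responders and treatment failures, will be followed for a period of one year".

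**Follow-up ended.** Section 6.3 deals with new systemic immunosuppression (IST) added for worsening cGVHD: "This will be considered a treatment failure, patient will be removed from study and treated according to institutional standard-of-care". Section 9.1 says: "Patients will be considered to be off study if any new systemic immunosuppressant therapy (including ECP) to treat worsening cGVHD is received". It continues: "No subsequent adverse or serious adverse event reporting will be done", and then: "Further follow up off study will be according to institutional requirements".

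**Endpoints that need the later data.** Section 10.2.2 lists non-relapse mortality, overall mortality and cumulative steroid dose as secondary endpoints. Section 10.1 gives a single analysis population: "All treated subjects". Section 8.2.2 and Appendix A schedule the steroid total at months 1, 2, 3, 6, 9 and 12.

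**Safety reporting elsewhere.** Section 7.1.1.5 has adverse events recorded to 30 days after the last dose, including every grade 4 and 5 event, with no cut-off at new therapy. Section 11.4.2 requires any death within 30 days of the last dose to be reported as an SAE, and asks for later SAEs judged related to study drug. Neither sentence exempts patients who have started new cGVHD therapy. Section 11.4.3 requires follow-up of SAEs that are unresolved when a subject's participation ends.

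**The concern.** The follow-up promise names treatment failures, and 6.3 and 9.1 remove that same group. A team working from 3.1 and 10.4 would collect deaths and steroid dose to month 12 in everyone. A team working from 6.3 and 9.1 would stop at the new therapy. The two could report different mortality and steroid results from the same patients.

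The patients without required data are selected by outcome, so the loss cannot be treated as random. Section 10.4 does not say whether removed patients are censored, counted to month 12 or handled in some other way.

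On safety, staff are told both to report and not to report certain events. A death 10 days after the last dose, in a patient who had just been given new IST, falls under the 11.4.2 reporting duty and under the 9.1 instruction to stop.

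**Working it through.** **The plan's own figure.** The plan gives no number for this point. Its sample size supplies the denominator, and it reproduces with the one-sided normal approximation in section 10.3 terms (0.55 versus 0.75, alpha 0.05, power 80%): [1.645·√(0.55·0.45) + 0.842·√(0.75·0.25)]² / 0.20² = 34.97, rounded up to 35. Nothing below bears on that calculation.

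**Text side by side: outcome data**

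| Topic | 3.1, 10.4, synopsis | 6.3, 9.1 |
|---|---|---|
| Follow-up of a failure | One year from start of therapy | Off study at new IST |
| Who sets later follow-up | The protocol | The institution |
| Month-12 vital status, cause of death | Needed for 10.2.2 | Not required |
| Steroid dose to month 12 | Scheduled in 8.2.2, Appendix A | Not required after removal |

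Section 7.1.1.4 may cover medications for 30 days after the last dose, which would recover a little of the steroid data. Failure-free survival is not shown to be affected, because the new therapy is itself the event.

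**Text side by side: safety**

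| Event after new IST | 9.1 | Elsewhere |
|---|---|---|
| Adverse event within 30 days of last dose | Not reported | Recorded (7.1.1.5) |
| Death within 30 days of last dose | Not reported | Reported as SAE (11.4.2) |
| Later SAE related to study drug | Not reported | Reported (11.4.2) |
| SAE already open at removal | Silent | Followed (11.4.3) |

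The general adverse event window in 11.4.2 has two end points joined by an *or*: 30 days after the last dose, and the start of new cGVHD therapy. It does not say which governs. Read with the second end point, it agrees with 9.1, so the conflict with 11.4.2 is confined to its death and related-SAE sentences.

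**Bound that needs no hazard assumption.** If k of 35 patients have unknown month-12 vital status, the best-to-worst range for 12-month mortality is k/35 wide.

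- Per patient: 1/35 = 2.9 points.
- Assume 12% to 30% fail: 35 × 0.12 = 4.2 and 35 × 0.30 = 10.5, so about 4 to 11 patients.
- Width: 4/35 = 11.4 points to 11/35 = 31.4 points.

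The 12% is the non-response rate of the earlier rituximab study in section 1.1.2 (3 of 25), not a rate of new IST. The 30% is an assumption.

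**Hypothetical bias if removed patients are censored.** Assumptions: a fraction f fails, with failure times uniform over months 1 to 9; the death hazard is λ before failure and HR·λ after. True 12-month mortality is set at 1 − √0.82 = 9.4%, from the earlier study's 82% two-year survival under a constant hazard. λ is solved to give that mortality, and the censored estimate is 1 − exp(−12λ). Understatement in percentage points:

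| f | HR 1 | HR 2 | HR 4 | HR 8 |
|---|---|---|---|---|
| 0.12 | 0 | 0.58 | 1.48 | 2.73 |
| 0.20 | 0 | 0.92 | 2.26 | 3.89 |
| 0.30 | 0 | 1.33 | 3.05 | 4.90 |

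For scale, the standard error is √(0.0945 × 0.9055 / 35) = 4.9 points.

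**Follow-up not required, same timing, ignoring deaths.** Mean failure time is month 5, so 12 − 5 = 7 months per failure.

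- No later coverage: 35 × f × 7 = 29.4, 49.0 and 73.5 of 420 patient-months for f = 0.12, 0.20 and 0.30 (7.0%, 11.7%, 17.5%).
- If 7.1.1.4 covers 30 days after removal: 35 × f × (7 − 30/30.44) = 25.3, 42.1 and 63.2 (6.0%, 10.0%, 15.0%).
- Scheduled visits falling after failure (months 1, 2, 3, 6, 9, 12): 0 + 0.125 + 0.25 + 0.625 + 1 + 1 = 3.0 of 6 per failure.

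These are months and visits without required recording, not milligrams of steroid lost.

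**The case against.** The strongest reply is practical. This is a one-centre trial, institutional follow-up continues after removal, and the centre will probably know who died. That stands as a limit on the likely loss. It does not settle the contradiction, because information known at the clinic is not study data unless the protocol requires it to be recorded.

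Section 11.4.5 mentions survival follow-up after progression, which suggests that such follow-up was contemplated. It does so only within a rule on reporting new malignancies, and no visit or procedure defines it. It should be aligned in the amendment but does not fill the gap.

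On safety, three limits are fair. The general window in 11.4.2 can be read as agreeing with 9.1. The clash with 7.1.1.5 arises only when new therapy starts on treatment or within 30 days of the last dose. Following an SAE that is already open under 11.4.3 is compatible with not reporting new ones, so that pair is uneasy rather than contradictory.

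The failure fractions, timing and hazard ratios are assumptions with no source in the documents. Only the 1/35 per patient of unknown status is free of them.

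**Conclusion.** The plan is wrong as written and should be fixed. Sections 6.3 and 9.1 contradict 3.1, 10.4 and the synopsis on follow-up of treatment failures, with consequences for overall mortality, non-relapse mortality and cumulative steroid dose. Section 9.1 also contradicts the death and related-SAE sentences of 11.4.2, and 7.1.1.5 within 30 days of the last dose.

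The true size cannot be derived, because the documents give neither a rate of new IST nor a censoring rule. Mortality would be understated only if removed patients are censored and die at a higher rate; with equal hazards the bias is zero, and the worst hypothetical case is about one standard error. The steroid total is understated only for failures given steroids after removal. The primary endpoint, failure-free survival and sample size are not shown to be affected.

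A separate minor point: the 30-day windows depend on what study drug means. Sections 5.1.1 and 6.2.3 use the term for ibrutinib, while 11.3 and 11.4.2 allow more than one agent. The last rituximab dose is listed at month 13.

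**What to change.** - **6.3 and 9.1:** state that new systemic IST counts as treatment failure but does not end data collection. For every treated subject, record vital status, cause of death, relapse, systemic IST and steroid dose to month 12.
- **10.4:** state that mortality follow-up is not censored at new IST, and that steroid dose is totalled to month 12 or death whether or not new IST is given.
- **9.1, 7.1.1.5, 11.4.2, 11.4.3:** reconcile into one reporting rule that keeps the 11.4.2 duties on deaths and related SAEs and says which end point applies once new cGVHD therapy starts. Align 11.4.5 with it.
- **Minor, separate:** define whether study drug includes rituximab and which study day month 13 means, and bring the 9.1 completion rule and Appendix A into line.

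No dosing or treatment-stopping rule is proposed. The cost is amendment wording, chart review or a phone contact for patients who fail, and some extra data entry at one centre. It needs no new patients or procedures.

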10.4. Efficacy Analysis Methods

This is a phase II trial evaluating the safety and efficacy of ibrutinib and rituximab as primary treatment of cGVHD. Efficacy and safety endpoints will be estimated according to the cumulative incidence and Kaplan-Meier methodology in the presence of competing risks. Outcomes will be compared to historical values based on the Gray's test and log rank test respectively. We plan to enroll 35 patients on this study. Patients will be formally monitored for 12 months to evaluate for outcome and safety endpoints (efficacy/safety visits at the completion of month 1, 2, 3, 6, 9, and 12). All other assessments will be done at the physician's discretion or institutional standards. All patients, responders and treatment failures, will be followed for a period of one year. The primary outcome measure will be the proportion of patients that are alive and off all systemic immunosuppression at 12 months following initiation of treatment. The primary endpoint will be estimated according to the Kaplan-Meier methodology in the presence of competing risks. Outcome will be compared to historical values based on the log rank test. Secondary outcome measures will be cGVHD response, cumulative steroid exposure, time to discontinuation of systemic immunosuppression, requirement for second-line cGVHD therapy, non-relapse and overall mortality, failure-free survival and safety. Secondary survival endpoints will be estimated according to the Kaplan-Meier methodology in the presence of competing risks, and outcomes will be compared to historical values based on the log rank test. Secondary time-to-event endpoints will be estimated according to cumulative incidence methodology, and outcomes will be compared to historical values based on the Gray's test (Gray 1988).

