11.4. Documenting and Reporting of Adverse Events and Serious Adverse Events by Investigators

11.4.1. Assessment of Adverse Events

Investigators will assess the occurrence of AEs and SAEs at all subject evaluation time points during the study. All AEs and SAEs whether volunteered by the subject, discovered by study personnel during questioning, detected through physical examination, clinically significant laboratory test, or other means, will be recorded in the subject's medical record and on the AEs CRF and, when applicable, on the Serious Adverse Event Report Form.

Each recorded AE or SAE will be described by its duration (i.e., start and end dates), severity, regulatory seriousness criteria (if applicable), suspected relationship to the investigational product, and any actions taken.

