11.4.2. Adverse Event Reporting Period

All AEs whether serious or non-serious, will be documented from the time signed and dated ICF is obtained until 30 days following the last dose of study drug or the start date of a new therapy for cGVHD. SAEs will be reported to the Sponsor Drug Safety via an SAE reporting form and will be recorded in the CRF from the time of ICF signing. Non-serious AEs will be recorded in the source documents from the time of ICF signing and will be recorded in the CRF from the first dose of study drug(s).

SAEs reported after 30 days following the last dose of study drug should also be reported if considered related to study drug. Resolution information after 30 days should be provided.

Progressive disease should NOT be reported as an event term, but instead symptoms/clinical

signs of disease progression may be reported. (See [Section 11.1.1](#))

All AEs, regardless of seriousness, severity, or presumed relationship to study drug, must be recorded using medical terminology in the source document. All records will need to capture the details of the duration and the severity of each episode, the action taken with respect to the study drug, investigator's evaluation of its relationship to the study drug, and the event outcome. Whenever possible, diagnoses should be given when signs and symptoms are due to a common etiology (e.g., cough, runny nose, sneezing, sore throat, and head congestion should be reported as "upper respiratory infection"). Investigators must record in the CRF their opinion concerning the relationship of the AE to study therapy. All measures required for AE management must be recorded in the source document and reported according to Sponsor instructions.

All deaths should be reported with the primary cause of death as the AE term, as death is typically the outcome of the event, not the event itself. Autopsy and postmortem reports must be forwarded to the Sponsor, or designee, as outlined above, if allowed per local regulatory guidelines.

If a death occurs within 30 days after the last dose of study drug, the death must be reported to the Sponsor as a SAE.

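### The completion rule in Section 9.1 ignores rituximab, so most or all of the 30 days after the month-13 infusion can fall after study completion with no scheduled contact

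*Combined protocol and SAP*

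**What the plan says.** - **Completion (Section 9.1).** Patients have "completed study follow up at 12 months or 30 days after the last dose of ibrutinib whichever comes last". Anything later is left to institutional requirements.
- **Treatment (Section 3.1).** Ibrutinib is given for 12 cycles of 28 days. Rituximab is given weekly for four weeks from study day 7 ± 3, then "q3months x 4 doses (months 4, 7, 10, 13". Appendix A allows ± 7 days around each maintenance dose.
- **Visits.** Section 3.1: "Patients will be formally monitored monthly for 12 months to evaluate for outcome and safety endpoints". Section 8.2.2: "Required testing for the response follow-up visits (months 1, 2, 3, 6, 9, 12". Section 10.4: "efficacy/safety visits at the completion of month 1, 2, 3, 6, 9, and 12". Appendix A allows the month-12 visit ± 7 days. No later visit or call is listed.
- **AE collection.** Under Section 11.4.2, AEs are documented "until 30 days following the last dose of study drug or the start date of a new therapy for cGVHD", and Section 7.1.1.5 sets a matching 30-day limit for CRF recording. Section 11.4.2 adds: "SAEs reported after 30 days following the last dose of study drug should also be reported if considered related to study drug". Section 11.4.1: "Investigators will assess the occurrence of AEs and SAEs at all subject evaluation time points during the study".
- **Safety endpoint (Section 10.2.2).** It is the incidence of grade 3 or higher AEs possibly or probably related to ibrutinib, rituximab or both. No time limit is given.

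**The concern.** The completion rule gives ibrutinib a 30-day tail but gives none to the other investigational agent, although that agent is planned to be given last. A patient can reach protocol-defined completion on or before the day of a protocol-planned infusion, and the following 30 days then contain no scheduled evaluation.

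What could be lost is limited. Reactions during the infusion are seen at the infusion. Related SAEs stay reportable. Section 7.1.1.5 never records expected grade 3 events without hospitalization, so these are not at issue. The exposed events are mainly unexpected, related grade 3 events without hospitalization and non-serious grade 4 events, which are likely to be missed if nobody asks. Whether this touches the safety endpoint depends on its time frame. As a 12-month incidence it does not change. As an incidence over the whole AE reporting period, some events could be missed.

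**Working it through.** The plan states no figure for this interval, so the check is a day count.

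**Inputs.** Day 1 is the first ibrutinib dose. Ibrutinib runs 12 × 28 days (3.1). The month-13 dose has a ± 7-day window, as does the month-12 visit (Appendix A). Assumption: no ibrutinib cycle is delayed.

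**Completion day under Section 9.1**
- Last ibrutinib dose: 12 × 28 = day 336.
- Ibrutinib limb: 336 + 30 = day 366.
- 12-month limb: 1 + 365 = day 366.
- Completion is day 366, or up to day 373 if taken at a month-12 visit 7 days late.

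With ibrutinib on schedule, the ibrutinib limb adds nothing to the 12-month limb.

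**Day of the month-13 dose.** The plan does not define month 13. Four calendar-month readings are:
- start of month 13: day 366;
- 12 months after the first rituximab dose: 7 + 365 = day 372;
- 12 months after the fourth weekly dose: 28 + 365 = day 393;
- end of month 13: 1 + 13 × 30.44 ≈ day 397.

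On the last three, the infusion itself comes 6, 27 or 31 days after nominal completion.

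**Uncovered days** = min(30, max(0, dose day + 30 − completion day)).

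| Nominal dose day | On time, completion 366 | On time, completion 373 | 7 days early, completion 366 | 7 days early, completion 373 | 7 days late, either |
|---|---|---|---|---|---|
| 366 | 30 | 23 | 23 | 16 | 30 |
| 372 | 30 | 29 | 29 | 22 | 30 |
| 393 | 30 | 30 | 30 | 30 | 30 |
| 397 | 30 | 30 | 30 | 30 | 30 |

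The lowest value is 359 + 30 − 373 = 16. The range is 16 to 30, and 30 at nominal dates.

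**28-day months instead**
- Start of month 13, 12 × 28 + 1 = day 337: 1 day uncovered (337 + 30 − 366); range 0 to 8 with the windows.
- 12 × 28 days after day 7, day 343: 7 days; range 0 to 14.
- End of month 13, 13 × 28 = day 364: 28 days; range 14 to 30.

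**Sensitivity to ibrutinib delay.** Section 9.1 covers the full window only if the last ibrutinib dose comes (dose day − 336) days late: 30, 36, 57 or 61 days on the four calendar readings. The documents do not say whether held doses are made up at the end. If 14 days were made up, completion moves to day 380 and the calendar-month range becomes 9 to 30. With 28 days it moves to day 394 and the range becomes 0 to 30. Early ibrutinib discontinuation leaves completion at 12 months.

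**Share of dosing.** 4 weekly + 4 maintenance = 8 planned rituximab doses, of which 1 is affected. This is a share of doses, not of missed events.

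**The case against.** Four points can be made for the plan as written.

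1. **The AE duty already exists.** Section 5.1 lists both agents, Section 11.1.4 uses a form that allows for more than one study drug, and Section 11.3 speaks of any study drug. The 30-day AE window therefore most naturally runs from the last dose of either agent. The bar on later AE reporting in Section 9.1 applies only to patients who go off study for new therapy. This stands, and it confines the point to a mismatch. It does not supply a contact at which the duty would be met.
2. **Capture is not confined to visits.** Section 11.4.1 goes on to include events that patients volunteer or that come to light by other means. This also stands, but it is passive ascertainment in patients who have formally completed the study.
3. **Study drug may mean ibrutinib alone.** The singular term is used that way in the ibrutinib dosing text (5.1.1.2, 5.1.1.4). Sections 9.1 and 11.4.2 would then agree with each other. The cost is that no AE window would follow the last rituximab dose, which leaves it less well covered.
4. **The day count is fragile and the consequence small.** Month is undefined, 28-day months can nearly close the gap, and made-up ibrutinib holds would shrink it. Section 3.1 supports reading safety as a 12-month figure, and patients who start new therapy leave the study, so fewer than 35 may receive the dose. All of this is fair and is why the point is minor. Calendar months remain the better reading: Section 3.1 counts ibrutinib in 28-day cycles but rituximab in months, and equates follow-up with one year.

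**Conclusion.** The concern holds as a minor design point. Section 9.1 leaves rituximab out of both limbs, and no contact is scheduled after month 12. On calendar-month readings with ibrutinib on schedule, 16 to 30 of the 30 days after the last infusion lie beyond completion. The low end needs a dose 7 days early together with a month-12 visit 7 days late. Over all readings of month 13 the range is 0 to 30.

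The documents do not show that safety data would be compromised. They show a completion rule out of step with the AE window that probably applies, for an agent whose related events the safety endpoint counts. Confidence is medium, because the size of the gap turns on undefined terms (month, study drug, the endpoint's time frame).

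**What to change.** - **Section 9.1:** define completion as the later of 12 months and 30 days after the last dose of ibrutinib or rituximab. Align the approximate one-year statement in Section 12.11.
- **Sections 7.1.1.5 and 11.4.2:** state that study drug means either agent.
- **Schedule (8.2.2 and Appendix A):** add one telephone AE contact 30 days after the last rituximab dose.

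At nominal calendar timing, completion moves from day 366 to dose day + 30, that is day 396, 402, 423 or 427. The added follow-up is 30, 36, 57 or 61 days, about 1 to 2 months, and the uncovered days become 0. The rest of the cost is protocol wording and one call for each patient who receives the month-13 dose, at most 35 unless patients are replaced.
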